8.6.2 Analysis of primary efficacy endpoint

The primary efficacy endpoint is defined as the change from baseline to week 12 of the Treatment period with respect to the weekly mean of the daily 24 hour Worst Itching Intensity NRS score. Testing of the primary efficacy endpoint will be 2-sided and conducted at the 5% error level.

The study will be considered positive if at least one safe and efficacious dose is identified. Effectiveness will be evaluated based on results of the primary efficacy analysis either using the estimate of treatment effect or the p-value of the hypothesis tests.

The null hypotheses H_{01} , H_{02} , H_{03} , and H_{04} given below will be tested against the alternative hypotheses H_{A1} , H_{A2} and H_{A3} respectively:

$$\begin{array}{llll} H_{01}: \mu_{D1} - \mu_P = 0, & H_{02}: \mu_{D2} - \mu_P = 0, & H_{03}: \mu_{D3} - \mu_P = 0, & H_{04}: \mu_{D123} - \mu_P = 0 \\ H_{A1}: \mu_{D1} - \mu_P \neq 0, & H_{A2}: \mu_{D2} - \mu_P \neq 0, & H_{A3}: \mu_{D3} - \mu_P \neq 0, & H_{A4}: \mu_{D123} - \mu_P \neq 0 \end{array}$$

Where μ_{D1} , μ_{D2} and μ_{D3} denote the mean change in Worst Itching Intensity NRS score from baseline to week 12 in the three active treatment dose groups and μ_P denotes the mean change from baseline to week 12 in the placebo group (placebo, P). D_1 denotes the CR845 0.25mg dose group, D_2 denotes the CR845 0.5mg dose group and D_3 denotes the CR845 1mg dose group and D_{123} denotes the doses (0.25, 0.5 and 1 mg) combined.

The weekly mean of the 24-hour Worst Itching Intensity NRS score will be defined as the sum of the daily Worst Itching Intensity NRS score reported during a specific week of the Treatment period (eg, Days 1 to 7, Days 8 to 14, Days 15 to 21, etc. till 78 to 84) divided by the number of non-missing scores for that week. If there are <4 non-missing daily worst itching scores during a specific week, the corresponding weekly mean worst itching score will be set to missing. The baseline score will be defined as the average of the daily 24-hour Worst Itching Intensity NRS scores over the last 7 days prior to randomization; at least 4 completed Worst Itching Intensity NRS worksheets will be required prior to randomization.

The primary efficacy variable will be analyzed using a mixed effects model with repeated measures (MMRM). The model will contain treatment, week, and treatment-by-week interaction as fixed effects; baseline score and renal disease status as covariates. For each

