Statistical Analysis Plan (SAP)

dose group, the treatment group difference vs placebo will be estimated as the simple contrast in the treatment effect at Week 12 of the Treatment Period. The treatment difference between all doses combined and placebo will be estimated using a similar approach.

For week 12, the adjusted least square means (LS means) and standard error (SE) from the model will be presented for each treatment group. The LS means estimate for the difference, standard error, 95% CI, and p-value will also be presented. The primary analysis will be conducted using the Full Analysis Set. A summary table including descriptive statistics (n, mean, SD, median, minimum, maximum) for the observed value and the change from baseline by treatment group will also be provided for the NRS score.

An unstructured covariance matrix structure will be used to model the within patient errors. If there are convergence issues, other structures that require fewer parameters will be applied in the following order: 1) heterogeneous Toeplitz, 2) autoregressive, 3) compound symmetry until convergence is attained. The Kenward-Roger approximation will be used to estimate the denominator degrees of freedom.

For the MMRM analyses, the missing Weekly NRS score will be imputed using a Multiple Imputation (MI) approach, assuming that patients who discontinue study drug early would have similar Worst Itching Intensity NRS scores as other patients in their respective treatment arm that have complete data. The details of missing data imputations described as below.

- Intermittent missing weekly NRS scores will first be imputed using the Markov Chain Monte Carlo (MCMC) method implemented with the SAS MI procedure, which is appropriate for non-monotonic missing data. Additional terms for baseline NRS score and randomization stratification category (as dummy 0/1 variables) will be added. This will be performed within each treatment group separately.
- The monotone missing weekly NRS values will then be multiply imputed with the SAS MI procedure using the monotone regression method. The regression model will include terms for treatment group, baseline NRS score, and randomization stratification category; all previous non-missing post-baseline NRS scores will be included in the model. Should convergence issues occur due to small cell size for the categorical covariates at either stage, they will be removed from the model.

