- The details of MNAR based imputation using SAS described under [Appendix H](#).

Descriptive statistics for the primary efficacy endpoint will also be provided by treatment group for each renal disease category (moderate CKD non-dialysis; severe CKD non-dialysis; severe CKD on dialysis). In addition, an analysis of the primary efficacy endpoint within each renal disease status will be performed using an MMRM model similar to the one implemented for the primary efficacy analysis but without renal disease status as a fixed effect. As the renal disease status was included a factor in the multiple missing data imputation for the primary analysis, the same multiple imputed datasets as created for the primary analysis and methods to combine results will be used for these analyses.

A linear trend test across the doses based on a MMRM model will also be presented to explore the dose response curve. The model will contain treatment as continuous variable (Placebo = 0 mg and other doses 0.25, 0.5, and 1.0 mg), week, and treatment-by-week interaction as fixed effects; baseline score and renal disease status as covariates. The estimate and p-value for overall effect of dose will be provided. An unstructured covariance matrix structure will be used to model the within patient errors.

Listings will be provided for Worst Itching Intensity NRS score for all the available visits.

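### The second and third covariance fallbacks in the SAP are named without week-specific variances; if they are reached and variability grows over time, they understate the Week 12 standard error (optional wording fix)

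*SAP*

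**What the plan says.** SAP 8.6.2 models 12 weekly means of the daily itch score ("Days 1 to 7, Days 8 to 14, Days 15 to 21, etc. till 78 to 84"). On the covariance it states: "An unstructured covariance matrix structure will be used to model the within patient errors". The fallback rule depends on convergence alone: "If there are convergence issues, other structures that require fewer parameters will be applied in the following order", and the order is "1) heterogeneous Toeplitz, 2) autoregressive, 3) compound symmetry until convergence is attained". The word heterogeneous is attached to Toeplitz only.

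For each dose, "the treatment group difference vs placebo will be estimated as the simple contrast in the treatment effect at Week 12". On degrees of freedom: "The Kenward-Roger approximation will be used to estimate the denominator degrees of freedom". No empirical (sandwich) variance appears in the readable text, and the appendices that hold the SAS code are redacted. The test level is also in 8.6.2: "Testing of the primary efficacy endpoint will be 2-sided and conducted at the 5% error level".

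The model is fitted to each of 100 imputed datasets and the results are combined with MIANALYZE. SAP 8.6.2 also plans a no-imputation sensitivity analysis and subgroup fits: "an analysis of the primary efficacy endpoint within each renal disease status will be performed using an MMRM model". The subgroup fits reuse the imputed datasets from the primary analysis. SAP 8.6.3 gives the same fallback list for Skindex-10 and 5-D Itch, measured at Weeks 4, 8, 10 and 12.

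Protocol 8.6.1 had instead chosen among structures by the Akaike criterion, which takes fit into account. The SAP's fixed order does not.

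**The concern.** Autoregressive and compound-symmetry structures, on their ordinary reading, assume that the change score varies equally in every week. If the true spread is smaller in early weeks than at Week 12, the fitted variance is an average over the 12 weeks, and that average is applied to a contrast that concerns Week 12 only. On completed data the estimated difference is the difference in Week 12 means (apart from covariate adjustment) whichever structure is fitted. What changes is its standard error, and with it the confidence interval and p-value. Kenward-Roger adjusts for estimating the covariance parameters within the chosen structure; it does not repair a structure whose variances are wrong.

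Growth in variability is plausible. Baseline is a covariate, and Week 1 directly follows the baseline week. If correlation with baseline fades over time, the variance that baseline leaves unexplained rises. The documents give no weekly SDs to confirm this.

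**Working it through.** **Inputs.** SD 2.6, 60 or 120 patients per arm and two-sided 5% are from SAP section 5. The 12 weekly means, the Week 12 contrast and the fallback order are from SAP 8.6.2. Assumptions: the Week 12 SD is 2.6, the Week 1 SD is varied, and the path between them is linear unless stated.

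**Plan's own figure.** A two-sided t-test with 60 per arm and effect size 0.52 has power 80.7%, against 80% in the SAP table. With 120 per arm and effect size 0.40 it is 87.0%, against 86%. The table reproduces to within 2 points.

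**Parameters at 12 weeks.** Unstructured: 12 × 13 / 2 = 78. Heterogeneous Toeplitz: 12 + 11 = 23. Heterogeneous AR(1) or compound symmetry: 12 + 1 = 13. The common-variance versions: 2 each.

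**Standard error on completed data.** The correct value is SD(Week 12) × √(2/n) = 2.6 × √(2/60) = 0.475, or 2.6 × √(2/120) = 0.336. A common-variance model reports SD(common) × √(2/n). For compound symmetry, SD(common)² is the mean of the 12 weekly variances. For AR(1) it is tr(R⁻¹Σ)/12 at the best-fitting correlation. With r = SD(common)/2.6, the actual two-sided error is 2[1 − Φ(1.96 r)].

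Example, Week 1 SD 1.3: the 12 squared SDs sum to 47.63, so the mean variance is 3.97, the common SD is 1.99, and r = 1.99/2.6 = 0.766. The error is 2[1 − Φ(1.50)] ≈ 13%.

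Compound symmetry, 60 per arm:

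| Week 1 SD | Mean variance | Common SD | r | SE | Two-sided error |
|---|---|---|---|---|---|
| 2.6 (constant) | 6.76 | 2.60 | 1.000 | 0.475 | 5.0% |
| 2.2 | 5.78 | 2.40 | 0.924 | 0.439 | 7.0% |
| 2.0 | 5.33 | 2.31 | 0.888 | 0.421 | 8.2% |
| 1.9 | 5.11 | 2.26 | 0.870 | 0.413 | 8.8% |
| 1.3 | 3.97 | 1.99 | 0.766 | 0.364 | 13.3% |
| 3.0 (falling) | 7.86 | 2.80 | 1.078 | 0.512 | 3.5% |

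AR(1) is almost the same: from 1.3 its SE is 0.364 to 0.369 and the error 12.8% to 13.3%, depending on the true correlation. If the SD rises early from 1.3 and then plateaus, the SE for either structure is 12% to 15% too small and the error is 8.5% to 9.7%.

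**Simulation check** (4,000 trials, four arms of 60). From 1.9, the mean reported SE was 0.412 (compound symmetry) and 0.413 (AR(1)), against an empirical 0.479; error was 9.2% for both. From 1.3, it was 0.364 and 0.367 against 0.481; error was 13.9% and 13.5%. With a free variance for each week, error was 4.7% to 5.6% across the settings.

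**Secondary scales** (compound symmetry). The same proportional growth is read at Weeks 4, 8, 10 and 12. From 2.0 the SDs are 2.16, 2.38, 2.49 and 2.60; mean variance 5.83, r = 0.929, so the SE is 7% too small and the error 6.9%. From 1.3 they are 1.65, 2.13, 2.36 and 2.60; mean variance 4.90, r = 0.852, so 15% and 9.5%. The unstructured matrix here has only 4 × 5 / 2 = 10 parameters.

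**Imputation.** With W the within- and B the between-imputation variance, the pooled variance is W + (1 + 1/100)B. The fallback shrinks W only, so the pooled SE is understated somewhat less than shown above.

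**The case against.** The strongest reply is that the plan is unlikely to arrive at these steps. A reader might infer that failure of the unstructured model leads straight to a common variance. It does not: heterogeneous Toeplitz comes first and keeps a variance for each week. The primary model runs on completed data for about 240 to 480 patients, and nothing in the documents suggests that both heterogeneous structures would fail there. This stands.

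A reader might also infer that the dialysis stratum makes fallback likely, since about 48 patients face 78 parameters. The documents do not support that. The subgroup fits use the imputed datasets, so 48 patients supply 48 × 12 = 576 observations, and the cap is a share of the total, about 96 patients at N = 480. In simulated complete data for 48 patients, an unstructured fit converged in 50 of 50 runs at each of two correlations, although not with the SAS algorithm. For the no-imputation sensitivity analysis and the interim analysis, no dropout or convergence rate is given, so fallback is possible there but not shown to be likely.

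Three further points stand. Growing variability is assumed. That steps 2 and 3 are homogeneous is read from the wording, because the code is redacted. Heterogeneous structures are no guarantee: under a random-slope truth with Week 12 SD 2.6, heterogeneous Toeplitz gave 2.29, though compound symmetry gave 2.00.

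The study is Phase 2, without multiplicity adjustment, and SAP 8.6.2 lets effectiveness rest on the estimate or the p-value. The estimate hardly moves. This lowers the priority but does not protect the reported interval and p-value.

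**Conclusion.** The point holds as a low-severity, conditional one. It needs three things together: both the unstructured and heterogeneous Toeplitz fits fail, the next steps are run with a common variance as their names imply, and variability grows over the 12 weeks. The Week 12 standard error for the itch score is then about 8% to 23% too small for a linear rise to 2.6 from between 2.2 and 1.3, with two-sided error of about 7% to 13%. For Skindex-10 and 5-D Itch it is about 7% to 15% too small under the same proportional growth from 2.0 or 1.3. These figures are for model-based errors on completed data, before the dilution from imputation.

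A reader might conclude that the primary result is at risk of a false positive. The documents do not support that: they give neither weekly SDs nor any sign that the first two structures would fail in the primary analysis.

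**What to change.** In SAP 8.6.2 and 8.6.3, name step 2 as heterogeneous first-order autoregressive and step 3 as heterogeneous compound symmetry, and keep Kenward-Roger for both. If a common-variance structure is wanted as a final resort, add it as a last step with an empirical (sandwich) variance.

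The cost is a few words in each section and the matching option names in the program. At 12 weeks each heterogeneous version has 13 covariance parameters instead of 2, still fewer than the 23 of heterogeneous Toeplitz, so the list still becomes simpler step by step. If the true SD is constant, the extra parameters are the only price. In the optional last step, the sandwich variance would replace Kenward-Roger. Nothing changes when the unstructured model converges.

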8.6 Efficacy analyses

This section describes the analysis to be conducted on the primary, secondary and additional efficacy variables. All the efficacy analyses will be performed using the full analysis set and data that is collected on or prior to the date of treatment discontinuation/completion. An analysis of the primary and secondary efficacy variables for the per-protocol population will be performed if more than 20% of the FAS patients are excluded in any of the treatment groups. Each CR845 dose group, will be compared against placebo for all the endpoints. In addition, a separate analysis comparing all CR845 doses pooled against placebo will be performed with respect to the primary and key secondary variables. Only the results for the all CR845 doses pooled group and the comparison with placebo will be presented from these analyses. An analysis of all CR845 doses pooled versus placebo with respect to the rest of the secondary variables may also be considered. A dose response analysis will be performed with respect to the primary and key secondary variables. Results for the primary and secondary efficacy variables will be presented by renal disease status (moderate CKD non-dialysis; severe CKD non-dialysis; severe CKD on dialysis).

Statistical Analysis Plan (SAP)

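### The renal-stratum analyses reuse imputations whose post-discontinuation step lists no treatment-by-stratum term, so any real differences between strata are partly shrunk

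*SAP*

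**What the plan says.** SAP 8.6.2 plans, for the final analysis, that "an analysis of the primary efficacy endpoint within each renal disease status will be performed using an MMRM model similar to the one implemented" in the main analysis, with renal status taken out of the model. The missing data are not imputed again: "As the renal disease status was included a factor in the multiple missing data imputation for the primary analysis, the same multiple imputed datasets" serve both purposes.

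The imputation has two steps.

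- **Intermittent gaps (MCMC).** "Additional terms for baseline NRS score and randomization stratification category (as dummy 0/1 variables) will be added", and "This will be performed within each treatment group separately".
- **Monotone missing weeks (regression).** "The regression model will include terms for treatment group, baseline NRS score, and randomization stratification category"; and "all previous non-missing post-baseline NRS scores will be included in the model". No treatment-by-stratum term is listed, and this step is not said to be run by arm.

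For both steps: "Should convergence issues occur due to small cell size for the categorical covariates at either stage, they will be removed from the model".

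SAP 8.6 limits efficacy analyses to "data that is collected on or prior to the date of treatment discontinuation/completion", so weeks after discontinuation fall to the monotone step. SAP 8.6.3 carries a similar missing-data treatment into the stratum analyses of the Skindex-10 and 5-D totals. It also derives the 3-point responder endpoint from the primary imputed datasets and examines that endpoint within strata.

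**The concern.** A main effect for stratum lets average itch differ between strata. It does not let the difference between drug and placebo vary by stratum. A separate MMRM per stratum does allow that, so the analysis model is richer than the model that supplied the imputed values. Those values then carry a treatment effect that is partly averaged over strata.

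The two steps also differ in a way the SAP does not explain. MCMC run within each arm, with stratum dummies, already allows stratum differences to vary by treatment. The monotone step does not, and it is the one that fills post-discontinuation data. The removal rule adds a second weakness: stratum, the whole ground for the reuse, may be dropped from the imputation model.

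At stake is how the stratum tables are read. The distortion runs toward apparent consistency: a stratum with no benefit would seem to have some, and a stratum with more benefit would seem to have less. Using one hundred imputations does not remove it.

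**Working it through.** **Inputs from the documents.** SD 2.6, 60 per arm, two-sided 5% test, effect size 0.52, about 1.4 points (SAP 5); allocation 1:1:1:1 and dialysis capped near 20%, 48 of 240 (SAP 3.2), hence 48/4 = 12 per arm.

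**Assumed, because not stated.** Dropout of 10, 20 or 30%; the other strata at 40% each; within-patient correlation either AR(1) 0.9 or compound symmetry 0.7; dropout early (0-3 weeks observed) or uniform over 12 weeks, unrelated to outcome; effect building linearly to Week 4 and then constant.

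**The plan's own figure.** Noncentral-t power at n = 60 per arm and d = 0.52 is 80.7%, against 80% stated. All 12 cells of the power table reproduce within 2 points. This point disputes none of them.

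**Large-sample simulation.** Four arms, 12 weekly scores, true Week 12 effects of -1.4, -1.4 and 0 points in the 40/40/20% strata, the same for each dose. Missing weeks were filled sequentially (a) with the SAP's listed terms and (b) by arm with stratum as covariate. Conditional means were used, which have the same expectation as the imputation average. The Week 12 contrast (mean of the three doses minus placebo) was then taken in each stratum and compared with the same data without dropout.

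Share kept = [null-stratum effect minus mean of the other two] with imputation, divided by the same quantity without dropout.

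| Dropout | Gap kept, listed terms | Gap lost | Shift of the null stratum toward benefit (points) | Gap kept, by arm |
|---|---|---|---|---|
| 10% | 91-96% | 4-9% | 0.03-0.10 | 99-101% |
| 20% | 82-92% | 8-18% | 0.09-0.22 | 98-101% |
| 30% | 74-87% | 13-26% | 0.15-0.30 | 100-101% |

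The larger losses come with early dropout. Worst case (30%, early, AR(1)): contrasts are -1.42, -1.41, 0.00 without dropout and -1.35, -1.34, -0.30 with the listed terms. The gap falls from 1.415 to 1.345 - 0.30 = 1.045, and 1.045/1.415 = 0.74.

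**Overall effect in that worst case.** Weighting by 0.4/0.4/0.2 gives 0.4(-1.42) + 0.4(-1.41) + 0.2(0.00) = -1.13 without dropout, and 0.4(-1.35) + 0.4(-1.34) + 0.2(-0.30) = -1.14 with the listed terms. The shifts cancel across strata.

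**Against sampling error.** SE of a dose-placebo contrast = 2.6 x sqrt(2/12) = 1.06 points in the dialysis stratum, and 2.6 x sqrt(2/24) = 0.75 with 24 per arm. The largest shift above, 0.30, is 0.30/1.06 = 0.28 of a standard error.

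**At the planned size.** In simulated trials of N=240 (24/24/12 per arm, effects 2/1/0, AR(1) 0.85, Week 12 ANCOVA within stratum), the listed terms shifted the extreme strata by 0.03-0.36 point beyond the no-dropout estimate. Adding treatment-by-stratum terms raised the dialysis-stratum RMSE from 1.08 to 1.16 (10% uniform), 1.07 to 1.23 (20% early) and 1.08 to 1.32 (30% early).

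**The case against.** Four objections have weight.

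- **Earlier scores carry part of the signal.** A reader might infer that every dropout is simply given the average treatment effect. The SAP does not support that: all previous weekly scores are predictors and already reflect the patient's own response. The pull is partial, which is why 74-96% of the gap survives. Intermittent gaps are not affected.
- **The code is not visible.** The SAP refers to Appendix F for the imputation code, and that appendix is redacted. An interaction or a by-arm run there cannot be excluded, although listing treatment as a model term points away from a by-arm run. The point rests on the listed terms.
- **No stated decision depends on these results.** A reader might link them to the interim goal in SAP 8.9 of finding doses that work in every stratum. But the by-stratum NRS output at the interim is summary statistics only (8.9.2.3), and the sample-size rule uses each dose's conditional power against placebo (8.9.1). Study success rests on the primary efficacy analysis and on safety.
- **The remedy costs precision.** With 12 dialysis patients per arm, the richer imputation removes most of the bias but raises RMSE. Borrowing across strata is a defensible choice if it is made knowingly.

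All four limit the reach of the point. None of them makes the stated reason for the reuse valid. The non-imputed stratum results already planned (descriptive tables, and an end-of-treatment responder comparison with Fisher's exact test) do not supply a Week 12 NRS contrast from a model free of this shrinkage.

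**Conclusion.** The point holds in a limited form. Having stratum as a main effect does not justify reusing the primary imputations for within-stratum treatment contrasts. If true effects differ, those contrasts are drawn together: about 4-9% of the gap at 10% dropout, 8-18% at 20% and 13-26% at 30%. These ranges depend on the assumed dropout, timing, correlation and stratum split. With equal true effects there is no shrinkage.

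The shift is well below the dialysis-stratum standard error of about 1 point, so it would seldom change the reading of that stratum alone. It is systematic, however, and favours a finding that the strata behave alike. It reaches the supportive final stratum analyses of the NRS, and the Skindex-10, 5-D and responder analyses that follow the same approach. A reader might infer that the primary contrast is biased as well. Nothing here shows that, and in the worst case worked above the shifts cancel overall. This is a minor, inexpensive improvement.

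**What to change.** 1. In SAP 8.6.2, delete the statement that the reuse is justified because renal status was a factor in the imputation. If the Appendix F code does contain an interaction or a by-arm monotone step, say so in the text; that would settle most of the point.
2. Beside the planned stratum results, report one analysis that allows treatment-by-stratum effects:
   - the Sensitivity analysis 1 model (MMRM, no imputation) within each stratum, which the SAP does not now specify by stratum; or
   - a separate imputation run with the monotone step by arm and stratum as covariate, or with the (4-1) x (3-1) = 6 treatment-by-stratum terms added.
3. State that stratum may not be removed from the imputation model for any dataset used in a stratum analysis.
4. Apply the same to the Skindex-10, 5-D and responder stratum analyses.

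**Cost.** One further PROC MI run or one further set of MMRM fits. The statistical cost is variance. At Week 12 a by-arm regression has 1 + 1 + 2 + 11 = 15 coefficients, from about 42-54 patients per arm at 30-10% dropout. The pooled model with six extra terms has 18 + 6 = 24, from about 168-216 patients, so it is the steadier of the two imputation options at N=240. The dialysis-stratum RMSE rises visibly either way, so the added analysis should stand beside the planned one and not silently replace it.
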